Maternal viral load (VL) levels provide a clear benchmark to guide clinical management and minimize risk of mother-to-child transmission. Limited evidence suggests that mothers with suppressed VL have very low risk of transmitting the virus to their infant. During *pregnancy*, estimates of the risk of mother-to-child transmission range from 0% to 5% when maternal VL is <1,000 copies/mL and 8.5%-37% when maternal VL is >1,000 copies/mL—with higher VL associated with greater risk of transmission. During *breastfeeding*, rates of mother-to-child transmission among mothers on ART range from 0.24%-3.1%, with a pooled risk of 1.8%, and higher rates among mixed-fed infants. Among the few studies tracking maternal VL and mother-to-child transmission through breastfeeding, all transmitting mothers had at least one detectable plasma VL (>1000 copies/mL) during the follow up period, and/or a documented treatment interruption.

Clinical intervention to address high maternal VL during pregnancy or breastfeeding can include enhanced adherence support, regimen switching, and enhanced infant prophylaxis. These interventions are only feasible if: 1) eligible patients receive VL tests, 2) results are promptly returned to health facilities, and 3) detectable VL results lead to clinical action. For women already on ART when presenting for antenatal care, Kenya's PMTCT guidelines call for a VL test as soon as pregnancy is confirmed. Women newly diagnosed with HIV per routine testing during pregnancy receive their first VL test 3 months after ART initiation. Repeat testing occurs every 6 months. VL testing should, therefore, reach most women 1-2 times during pregnancy and 1-4 times during breastfeeding. National data on the uptake of these tests in PMTCT have not been published, but our pilot data of records reviewed at 4 Kenyan hospitals indicate insufficient VL testing among pregnant (49.8%) and breastfeeding (by 6 months postpartum) (21.7%) women, an average of 2.3 weeks' turnaround time to get VL test results, and few patients (36.0%) being notified of their results. Only 28.9% of patients with detectable viral loads had any documented evidence of clinical action taken. Delays in timely clinical action after detectable VL results were cited in PEPFAR's Kenya Country Operational 2017 Plan as a key barrier in Kenya, and as a target for interventions.

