### 4.0 Objectives

**General Objectives:** We will evaluate the impact of the HITSystem 2.1 system-level intervention in a pragmatic clinical setting on two primary outcomes: complete, guideline-adherent PMTCT retention (**Objective 1**) and viral suppression (**Objective 2**) through 6 months postpartum. We will also evaluate implementation outcomes (**Objective 3**) and the cost-effectiveness of HITSystem 2.1 (**Objective 4**).

Specific objectives:

**Objective 1:** Evaluate the efficacy of HITSystem 2.1 to increase the proportion of women who receive complete PMTCT services through 6 months postpartum, per Kenyan national guidelines.

*Hypothesis: Pregnant women receiving HITSystem 2.1 will have a significantly higher completion rate for guideline-adherent PMTCT services compared to pregnant women receiving SOC.*

**Objective 2:** Evaluate the efficacy of HITSystem 2.1 to increase viral suppression (<1,000 ml/copies) through 6 months postpartum, per Kenyan national guidelines.

*Hypothesis: Sites implementing HITSystem 2.1 will have a significantly lower proportion of women with a detectible VL at delivery and 6 months postpartum compared to those receiving SOC.*

[figure not shown]
**Objective 3:** Evaluate the reach, effectiveness, adoption, implementation fidelity and maintenance (REAIM model) of HITSystem 2.1 using system data and surveys with providers and patients.

**Objective 4:** Evaluate the costs and cost-effectiveness of HITSystem 2.1 for increasing: 1) complete PMTCT retention, 2) viral suppression, and 3) modeled estimates for pediatric HIV infections averted. Cost effectiveness will be driven by estimating the proportion of women averting a detectible VL result during pregnancy or postpartum as a proxy for perinatal transmissions averted.

*Hypothesis: HITSystem 2.1 will be cost-effective for PMTCT retention and viral suppression, based on WHO criteria for life years saved.*

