We will use the number of perinatal transmissions observed in the study (intervention v control), but since the actual numbers are expected to be low, we will also rely on viral suppression data to estimate transmission on a larger scale. Based on literature assessments of maternal viral load and perinatal HIV transmission of HIV, we will estimate rates of transmission at 2.5% and 22.5% for virally suppressed and unsuppressed women, respectively. We will use the estimated number of transmissions in intervention and control sites to compute savings from pediatric infections averted (lifetime ART costs for infants, HIV-related mortality). Data collected on ART adherence and VL testing will be used to calculate the wastage saved by HITSystem 2.1. VL test costing data have been assessed at the national level, and costing estimates for maternal and pediatric ART are available by regimen, but outcome data from the proposed study are needed to adequately calculate the benefits of HITSystem 2.1. Anticipated costs, costs savings, and benefits are outlined below, Table 8.

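### The modelled transmission rates come from the pregnancy literature, but the viral-load measure they are to be used with includes postpartum results, and breastfeeding transmission is not modelled separately

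*Combined protocol and SAP*

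**What the plan says.** All places are in the combined protocol and SAP.

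- **Objective 4 specific methods** sets the rates: "we will estimate rates of transmission at 2.5% and 22.5% for virally suppressed and unsuppressed women". The stated basis is "Based on literature assessments of maternal viral load and perinatal HIV transmission of HIV", with references 22-26. No VL time point is named.
- **1. Introduction/Background** uses those same references for pregnancy: "estimates of the risk of mother-to-child transmission range from 0% to 5% when maternal VL is <1,000 copies/mL" and "8.5%-37% when maternal VL is >1,000 copies/mL". It treats breastfeeding apart, from references 27-29: "rates of mother-to-child transmission among mothers on ART range from 0.24%-3.1%, with a pooled risk of 1.8" percent. That figure covers mothers on ART and is not split by VL. It adds that "all transmitting mothers had at least one detectable plasma VL (>1000 copies/mL) during the follow up period" and/or a documented treatment interruption.
- **4.0 Objectives**, Objective 4, says cost-effectiveness will be driven by "estimating the proportion of women averting a detectible VL result during pregnancy or postpartum as a proxy for perinatal transmissions averted".
- **Objective 4 specific methods** also names the primary driver as the reduction in infants found HIV-positive at the first test, at six weeks. It plans sensitivity analyses that include mother-to-child transmission rates, and it uses transmissions observed in the trial, which are expected to be few.
- **Objective 2 specific methods** collects VL at two points: at delivery (within four weeks) and postpartum, by about six months.

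**The concern.** The three statements about Objective 4 do not describe one model. The rates belong to pregnancy. The VL measure in section 4.0 spans pregnancy and postpartum. The named primary driver is a six-week infant test, and viraemia that begins after that test cannot have caused a positive result at it.

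Followed as written, each averted detectable result is credited with the same gain, 22.5% minus 2.5%, whenever it occurs. A woman suppressed at delivery and detectable only at six months would be given a risk drawn from pregnancy studies. A woman detectable at delivery who stays detectable would be given no further risk for breastfeeding.

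Modelled infections averted feed the savings in lifetime infant ART and HIV-related mortality and the infant QALYs in Table 8. Because observed transmissions are expected to be few, the model will carry much of the estimate. The cost-effectiveness conclusion could move for a reason unrelated to the trial data.

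**Working it through.** **Inputs.** Transmission rates of 2.5% and 22.5% (Objective 4 methods). Pregnancy ranges of 0-5% and 8.5-37%, and breastfeeding risk of 0.24-3.1%, pooled 1.8% (Introduction). Expected detectable shares of 35% under standard of care and 11% with HITSystem 2.1 (sample size considerations for Objective 2; Table 5). The share of averted detectable results that are postpartum only is not given; 25% and 50% are assumed below.

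**1. Where the rates come from.** Midpoints of the pregnancy ranges: (0 + 5)/2 = 2.5%, and (8.5 + 37)/2 = 22.75% against the stated 22.5%. The protocol does not say it used midpoints, so this is an inference. The shared references already point to pregnancy.

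**2. What the plan credits.** Gain per averted detectable result: 0.225 − 0.025 = 0.20. Per 1,000 women: 1,000 × (0.35 − 0.11) × 0.20 = 48 infections averted.

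**3. Would the rates fit breastfeeding?** Applied to the expected shares they give 0.35 × 0.225 + 0.65 × 0.025 = 9.5% and 0.11 × 0.225 + 0.89 × 0.025 = 4.7%. Both exceed the top of the protocol's breastfeeding range, 3.1%.

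**4. Ceiling on the breastfeeding rate among detectable women.** If all breastfeeding transmission comes from detectable women, their rate is the overall rate divided by the detectable share. Any transmission from suppressed women lowers it.

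| Overall breastfeeding risk | Share 35% | Share 23% (mean of 35% and 11%) | Share 11% |
|---|---|---|---|
| 0.24% | 0.7% | 1.0% | 2.2% |
| 1.8% | 5.1% | 7.8% | 16.4% |
| 3.1% | 8.9% | 13.5% | 28.2% |

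At 35% every entry is well below the credited 20 points. The credit stops being too large once the share falls to 1.8/20 = 9% (pooled rate) or 3.1/20 = 15.5% (top rate). The bottom-right cell is past that point.

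**5. Counting only the postpartum-only error.** Infections averted per 1,000 = 240 × [(1 − f) × 0.20 + f × r], where f is the postpartum-only share and r the rate from step 4. With r = 5.1% to 16.4%:
- f = 25%: about 39 to 46.
- f = 50%: about 30 to 44.
- f = 50% and r = 28.2%: 240 × (0.100 + 0.141) = about 58, above the plan's 48.

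**6. Counting breastfeeding risk in women who stay detectable as well.** Assume f = 50% and that the other half remain detectable postpartum. An infant must escape infection in pregnancy to be infected later, so the gains are 0.20 + 0.775r (detectable in both periods) and 0.975r (postpartum only):

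240 × [0.5 × (0.20 + 0.775r) + 0.5 × 0.975r] = about 35 at r = 5.1% and about 58 at r = 16.4%.

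This range straddles 48.

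**The case against.** The strongest reply is that the misapplication is inferred. The paragraph that sets the rates names no VL time point and speaks of perinatal transmission. The primary driver is the six-week test, and a secondary driver concerns VL results returned by 36 weeks of gestation. All of this fits a pregnancy-and-delivery model, for which pregnancy rates are suitable. This stands as far as it goes: if the sponsor means VL at delivery only, one sentence settles how the rates are applied. But section 4.0 says otherwise, and no section gives a postpartum rate.

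A second reply is that the sensitivity analyses vary transmission rates and that observed transmissions are also used. That helps in part. The lowest result in step 5 for the pooled rate, about 30 per 1,000, is 0.126 per averted result, equivalent to an unsuppressed rate of about 15%, inside the 8.5-37% range. The protocol does not say what range will be used or whether the two periods will be varied apart, and the base case would be unchanged.

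A reader might infer from step 5 that the plan overstates infections averted by about 1.1 to 1.6 times (48/44 and 48/30). The documents do not support that. It counts one error and leaves out the opposing one in step 6. It also divides an average over all mothers on ART in other cohorts by this trial's planning shares, which rest on 5/16 and 2/22 women adjusted for loss to follow-up. And it drops the treatment-interruption qualifier in the Introduction.

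**Conclusion.** The sections on Objective 4 are inconsistent about which VL result feeds which outcome. Read together, they give a pregnancy risk to women detectable only postpartum and leave breastfeeding transmission without its own rate. Modelled infections averted may therefore be biased.

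For postpartum-only results at the expected standard-of-care share, overstatement is likely: at most about 5% (1.8%/35%) or 9% (3.1%/35%) is implied, against 22.5%. This rests on that 35% share being a fair match for the breastfeeding cohorts. For the model as a whole neither direction nor size is fixed: the illustrations run from about 30 to 58 per 1,000 around the plan's 48. The missing quantities are the postpartum-only share, a breastfeeding rate by VL status, and how many women remain detectable after delivery. The point concerns Objective 4 only and does not touch the two primary outcomes.

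**What to change.** - Reconcile section 4.0 with the Objective 4 specific methods: state which VL measurement feeds which infant outcome, and which outcome is the primary driver.
- Apply 2.5% and 22.5% only to VL status at delivery.
- Model breastfeeding transmission separately for all women, including those detectable at delivery, by postpartum VL status. Use a sourced rate specific to VL status.
- Check that the overall modelled breastfeeding risk is compatible with the Introduction's 0.24-3.1%. Do not use that range directly as the rate for detectable women: it is an average over all mothers on ART and would be too low for them if transmission is concentrated there.
- In the planned sensitivity analysis, state the ranges and vary the pregnancy and breastfeeding rates separately.

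The cost is one more sourced input and a small change to the model. VL is already to be collected at delivery and postpartum, so no new data collection is needed. The estimated benefit may change in either direction.

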#### Objective 4 specific methods

Evaluate the costs and cost-effectiveness of HITSystem 2.1 for increasing: 1) complete PMTCT retention, 2) viral suppression, and 3) modeled estimates for pediatric HIV infections averted

We will establish a unit associated with each type of resource used, estimate the dollar value of each resource, calculate the number of units used, and multiply the units of resources used by the dollar cost for each. Costs (licensing, computing/telecommunication, and personnel/training) will then be summed to derive the low, medium, and high estimates of the total cost of the intervention. Research (research personnel, remuneration) costs will be calculated separately. We will then remove the costs saved with HITSystem 2.1 from the gross program cost. We will conduct sensitivity analyses with a range of estimates for HIV prevalence, rates of viral suppression, mother-to-child transmission rates, and patient volume to assess variations in cost effectiveness outcomes driven by key epidemiologic or demographic data.

The primary driver of the proposed cost-effectiveness analyses for HITSystem 2.1 will be the estimated reduction in the proportion of infants diagnosed with HIV at the initial test at 6-weeks of age. Since maternal nonadherence to ART, long turn-around time for VL results, and failure to take clinical action based on detectable VL results represent wasted investments in PMTCT services, secondary drivers of the cost-effectiveness analyses will be the proportion of (1) women with optimal ART adherence during the antenatal and post-partum periods, (2) women with VL results returned in time for prompt clinical action (by 36 weeks gestation) and (3) detectable VL results that trigger guideline-adherent clinical action.

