**Table 8. Anticipated costs, savings and benefits for cost-effectiveness analysis**

| HITSystem 2.0 Intervention Costs  | Anticipated Cost Savings   | Anticipated Benefits                         |
|---|--|--|
| training, licensing, internet, computer/modem, implementation support
*costs to health system may increase with higher rates of VL testing | Reduced: delayed/un-returned VL results, detectable VL results w/out clinical action, poor maternal ART adherence, pediatric infections and associated costs | QALY saved (infants)
QALY saved (mothers) |

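### As written, Objective 4 deducts wastage saved from programme cost although that money is still spent, which biases cost-effectiveness towards HITSystem 2.1

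*Combined protocol and SAP*

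**What the plan says.** All of this is in the combined protocol and SAP.

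- **Gross cost** (Objective 4 specific methods): "Costs (licensing, computing/telecommunication, and personnel/training) will then be summed to derive the low, medium, and high estimates" of total intervention cost.
- **Netting rule** (same paragraph): "We will then remove the costs saved with HITSystem 2.1 from the gross program cost".
- **Why wastage matters** (next paragraph): poor maternal adherence, slow VL results and inaction on detectable results "represent wasted investments in PMTCT services". Three proportions on these steps are then named as secondary drivers of the analysis.
- **Wastage as a quantity** (same section): "Data collected on ART adherence and VL testing will be used to calculate the wastage saved by HITSystem 2.1". No formula or unit value follows.
- **Table 8, savings column**: "Reduced: delayed/un-returned VL results, detectable VL results w/out clinical action, poor maternal ART adherence, pediatric infections and associated costs".
- **Table 8, benefits column**: QALYs for infants and for mothers, the first entry being "QALY saved (infants").
- **Effects to be costed**: "1) complete PMTCT retention, 2) viral suppression, and 3) modeled estimates for pediatric HIV infections averted".
- **Paediatric infections**: modelled transmissions will be used to "compute savings from pediatric infections averted (lifetime ART costs for infants, HIV-related mortality").

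A note in Table 8's cost column accepts that health-system costs may go up if more VL tests are done. The Objective 4 hypothesis in section 4.0 judges cost-effectiveness by WHO criteria on life years.

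**The concern.** A cost saving in a cost-effectiveness ratio should be a resource that is no longer used. The three wastage items are not of that kind as described. They measure how much benefit is obtained from tests and drugs already paid for. Section 2 makes the same observation when it says that poor handling of results lowers the return on VL testing investment. A better return is an effect, and the plan already has effects that capture it. Deducting it from cost as well rewards the intervention twice for one gain.

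At stake is the Objective 4 result, which the Abstract ties to the case for national dissemination. Objectives 1 and 2 are not affected.

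**Working it through.** The plan states no net cost, savings total or cost-effectiveness ratio, so there is no headline figure to reproduce. The check traces the items through the rule, then uses the planning rates for direction and scale.

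**1. One VL test.** Let a test cost *c*. If a detectable result is ignored, spending is *c*. If it is acted on, spending is still *c*. The change in spending is *c* − *c* = 0. On the natural reading of wastage, *c* moves from wasted to saved, so a credit of *c* is booked. For ART, a missed refill that is later collected raises drug spending, yet adherence improves and the credit is positive.

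**2. The ratio.** Per woman, let G be gross programme cost, D added VL tests and ART, A resources really avoided, W the wastage credit beyond A, and E the effect.

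- Without the credit: (G + D − A) / E
- With the credit: (G + D − A − W) / E
- Difference: −W / E

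E is the same in both lines. For any W > 0 the ratio falls, whatever G, D and A are.

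**3. Supporting rates** (sample size considerations for Objective 2 and Table 5):

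- Control: 0.76 × 31.25% + 0.24 × 1.5 × 31.25% = 35.0%, as stated.
- Intervention: 0.76 × 9.09% + 0.24 × 1.5 × 9.09% = 10.2%, as stated, rounded by the plan to 11%.

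**4. Effect from the plan's transmission rates** (2.5% if suppressed, 22.5% if not):

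- Control: 0.35 × 22.5% + 0.65 × 2.5% = 9.5%
- Intervention: 0.11 × 22.5% + 0.89 × 2.5% = 4.7%
- Difference: 4.8 points, or 48 infections averted per 1,000 women, with or without the credit.

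**5. Effect of each USD 1 credited per woman:**

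| Outcome | E per woman | Fall in ratio, 1 / E |
|---|---|---|
| Infection averted | 0.048 | USD 20.8 |
| Woman suppressed (35% − 11%) | 0.24 | USD 4.2 |
| Complete PMTCT (planned 20 points) | 0.20 | USD 5.0 |

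For complete PMTCT the overlap is direct: Table 6 makes VL testing and action on a detectable result components of that outcome.

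**6. Can W be sized?** Not from the documents. As an illustration only, assume one VL test per woman at USD 10 to 40, a wasted share that falls by 20 to 40 points, and an ART credit of USD 0 to 50 per woman. Then W runs from 10 × 0.20 + 0 = USD 2 to 40 × 0.40 + 50 = USD 66. Take G from two budget lines, usage and training: (43,800 + 8,300) / 726 = USD 72, where 726 is half of 1,452 and assumes equal arms. This G is partial, since it leaves out staff and implementation support. With D and A set to zero, cost per infection averted is 72 / 0.048 = USD 1,500 without the credit. With it, the figure is between 70 / 0.048 = USD 1,458 and 6 / 0.048 = USD 125, a fall of 3% to 92%. So wide a range says only that the result depends on unit costs the plan does not give.

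**7. Would the plan reveal it?** The listed sensitivity analyses vary prevalence, suppression, transmission and patient volume. The low, medium and high estimates vary programme cost. Neither removes the credit. The listed cost components also do not name added VL tests or ART, despite the Table 8 note.

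**The case against.** The best defence is that no net-cost formula is written. The netting sentence is in the costing paragraph, while wastage is introduced in the next one, where the secondary drivers are proportions that look like process outcomes. This stands as a caution: the rule is read from several places together. But Table 8 puts the wastage items under a savings heading, the text says wastage saved will be calculated, and nothing limits costs saved to spending avoided. An analyst following the text would deduct them.

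Four stronger conclusions are tempting, and the documents do not support them.

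- **That no spending could be avoided.** Returned results might spare repeat tests, and better adherence might spare regimen switches; the plan says ART costs are available by regimen. These would be real offsets if measured. The plan does not describe them, but does not exclude them.
- **That mortality is certainly counted twice.** This rests on one parenthesis. Table 8's savings column speaks only of infections and associated costs, so the parenthesis may mean care costs, or consequences to be modelled through QALYs.
- **That a money total follows** from applying the pilot's 36.0% patient-notification rate to the USD 20.6 million national VL spending in section 2. The plan never applies wastage to that sum, and patient notification is a different step from return of results.
- **That the hypothesis could be met through accounting alone.** No ratio, threshold or unit cost is given that would show this.

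It is also fair that Objective 4 is not a primary outcome, that the budget includes consultants for cost-effectiveness guidance, and that netting lifetime paediatric ART for infections averted is legitimate.

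**Conclusion.** The point holds. Followed as written, the plan credits as savings money that is still spent, while the same gain is counted as suppression, infections averted and QALYs. The direction is certain for any credit beyond resources really avoided: net cost falls, the effect does not change, and the comparison tilts towards HITSystem 2.1. The total size is unknown. What follows from the planning rates is about USD 21 less per infection averted for each USD 1 credited per woman, assuming 35% versus 11% detectable VL and the plan's transmission rates.

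The mortality part is conditional. If the parenthesis means the value of deaths averted, it is counted again in QALYs or life years. If it means care costs, it is a legitimate offset that needs to be named. This should be settled before the cost analysis is run.

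**What to change.** In Objective 4 specific methods and Table 8:

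1. Define costs saved as measured or modelled resource use actually avoided, net of added VL tests and ART. Examples are lifetime paediatric ART and care for infections averted, and repeat VL tests or regimen switches avoided if measured.
2. Move the three wastage items out of the savings column. Report them as process outcomes, or as a scenario outside the base case.
3. Count mortality only in QALYs or life years. If care costs are meant, say so.

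The cost is a change of wording in the costing plan. VL tests and refills are already to be recorded in both arms, so no visit, sample or participant is added. The downside for the sponsor is that the cost-effectiveness ratio becomes less favourable.
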